4.3 Exploratory objectives

- To investigate the relationship between baseline subject characteristics, such as clinical diagnosis (PHN or DPN)
 , and the change in NPRS after oral LAT8881 treatment, compared with placebo
- To investigate the relationship between plasma LAT8881 concentrations and the change in mean pain score in subjects with NP
- To investigate the impact of variability in NPRS scores during the first baseline period on the difference between baseline and 4 week NPRS scores after LAT8881 or placebo

5. Study design

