9.5 Exploratory endpoints

- Association between change in mean NPRS from baseline to the end of four weeks treatment and selected subject baseline characteristics, including clinical diagnosis and pre-treatment QST parameters
- Change from baseline in specified QST parameters to the end of 4 weeks treatment, in each treatment period
- Correlation between plasma LAT8881 concentration and the change in mean NPRS from baseline to the end of four weeks treatment in PK subjects
- Change in mean NPRS score from baseline to the last week of each treatment period, after omission of subjects with the 25% most variable first baseline NPRS scores

10. Study measurements

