13.8 Analysis of exploratory endpoints

Exploratory analyses will be undertaken to determine the relationship between change in mean NPRS from baseline to the end of four weeks treatment and baseline parameters, such as the clinical diagnosis (PHN or DPN) and baseline QST parameters. The effect of treatment on changes in QST parameters from baseline to the end of four weeks treatment will also be analysed.

The effect of the variability in NPRS scores within the first baseline period on the ability to detect a treatment difference will be examined.

The relationship between plasma LAT8881 and NPRS in PK subjects will also be investigated.

The approaches to these investigative analyses will be detailed in the statistical analysis plan.

14. Study management

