3.3 Exploratory Objectives

1. To investigate the relationship between baseline subject characteristics, such as clinical diagnosis (PHN or DPN) and [REDACTED], and the change in NPRS after oral LAT8881 treatment, compared with placebo
2. To investigate the change from baseline on [REDACTED] after four weeks treatment with oral LAT8881, compared with placebo
3. To investigate the relationship between plasma LAT8881 concentrations and the change in mean pain score in subjects with NP
4. To investigate the impact of variability in NPRS scores during the first baseline period on the difference between baseline and 4 week NPRS scores after LAT8881 or placebo

4 Study Design

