11.6.1.2 Mixed Effect Regression Model

A mixed effects regression model using a covariance pattern will be fitted to the absolute change from baseline mean NPRS scores at weeks 1, 2, 3 and 4 within each treatment period for the PP population. This analysis will provide the results for the primary efficacy endpoint (change from baseline to week 4) and for the secondary endpoint (change from baseline to weeks 1, 2 and 3).

The model will have fixed effects for period, week, treatment and the interaction between week and treatment. Baseline mean pain score within each period by treatment combination will be included as a covariate. A random effect for subject will be included to capture the repeated measures nature of the design.

Least squares means and corresponding 95% confidence intervals (CI) will be presented for the mean change from baseline for LAT8881, Placebo and difference between LAT8881 vs. placebo at each visit.

P-values for testing the null hypothesis that the difference in least squares means between LAT8881 and placebo at each visit is 0 will be declared statistically significant if the p-value < 0.05.

The covariance pattern will take into account the covariance between observations in different treatment periods and the covariance between observations within the same period (i.e between weeks).

```
proc mixed data=;  
class <subject> <study period> <treatment> <week>; model  
<change> = <baseline> <study period> <week> <treatment>;  
random <subject> <subject>*<period>; lsmeans <treatment>  
<week> / pdiff;  
run;
```

The model will also be fitted to the absolute change from baseline in mean NPRS ratings for the FAS population. Extent of sensitivity analyses of missing data patterns to be undertaken will be decided during the blinded review meeting. In DDP: Tables 14.2.2.1 to 14.2.2.2

11.6.1.2.1 *NPRS at timepoints*

A mixed effects regression model using a covariance pattern will be fitted to the absolute change from pre-dose NPRS scores at timepoints 0.5, 1, 2, 4 and 6 hours post-dose at baseline and week 4 visits within each study period for the per-protocol subjects with NPRS collected at timepoints in baseline and week 4 visits.

The model will have fixed effects for period, week, timepoint and the interaction between week and timepoint. Pre-dose pain score within each week will be included as a covariate. A random effect for subject will be included to capture the repeated measures nature of the design.

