11.6.2.5 NPRS and baseline covariates

The mixed effects linear regression model will be repeated for the change from baseline in NPRS scores by including additional covariate: clinical diagnosis (PHN, DPN). Further analyses will be decided and performed in a post-hoc manner post database lock.

In DDP: Table 14.2.10.1

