11.7.3.4 Electrocardiogram Assessments

Number and percentage of subjects with overall findings (Normal, Abnormal Not CS and Abnormal CS) will be summarized by treatment overall and within each study period and visit. Percentages will be based on safety population.

In DDP: Table 14.3.6.1

ECG findings will be listed by treatment sequence, subject ID, treatment period and visit.

In DDP: Listing 16.2.9.3

12 Changes to Planned Analyses

- Mixed Effect Regression analyses for change from baseline in NPRS mean scores is combined for weeks 1-4 within the same model, instead of week 4 and weeks 1-3 separately as defined in study protocol.
- McNemar's test is included to compare proportion of subjects achieving $\geq 30\%$ and $\geq 50\%$ reduction in mean NPRS scores across study periods.
- Analysis of covariance is included to see the effect of treatment and placebo in maximum reduction from baseline adjusting for baseline NPRS mean scores and time taken to reach maximum reduction.
- Mixed Effect Regression analyses for change from baseline in NPRS mean scores including clinical diagnosis (PHN, DPN) and baseline [REDACTED] as additional covariates is

considered as secondary analyses instead of exploratory analyses since subgroups PHN and DPN were considered clinically relevant.

- PK Analyses is not included in this Statistical Analysis Plan, and will be done separately. PK Population is replaced with Per-Protocol population for subjects with NPRS assessments taken at timepoints in baseline and Week 4 visits.

13 Index of Tables, Listings and Graphs

Refer LAT-NP-001_Data Display Plan (Ver: 2.00) for the list of Tables, Listings and Graphs.

14 References

1. ICH. ICH Harmonized Tripartite Guideline: Statistical Principles for Clinical Trials E9. 1998.
2. ICH. ICH Harmonized Tripartite Guideline: Structure and Content of Clinical Study Reports E3. 1995.

15 Appendices

15.1 painDETECT questionnaire

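### The PHN/DPN analysis adds diagnosis to the NPRS model without a treatment-by-diagnosis term, so it cannot estimate whether the LAT8881 effect differs by diagnosis

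*SAP*

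**What the plan says.** The objective in Protocol 4.3 begins "To investigate the relationship between baseline subject characteristics, such as clinical diagnosis (PHN or DPN"). SAP 3.3 carries the same objective and ends it with "and the change in NPRS after oral LAT8881 treatment, compared with placebo". The matching endpoint in Protocol 9.5 (repeated in SAP 7.5) is worded more loosely and does not mention placebo: "Association between change in mean NPRS from baseline to the end of four weeks treatment and selected subject baseline characteristics".

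Protocol 13.8 leaves the method to the SAP: "The approaches to these investigative analyses will be detailed in the statistical analysis plan". SAP 11.6.2.5 supplies it by repeating the NPRS model "by including additional covariate: clinical diagnosis (PHN, DPN"). It gives no code for this model and adds: "Further analyses will be decided and performed in a post-hoc manner post database lock".

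The model being repeated is that of SAP 11.6.1.2: "The model will have fixed effects for period, week, treatment and the interaction between week and treatment". Baseline for each period is a covariate and subject is random. SAP section 12 explains the analysis's new status: it is "considered as secondary analyses instead of exploratory analyses since subgroups PHN and DPN were considered clinically relevant".

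**The concern.** An objective framed relative to placebo asks whether the drug-placebo difference depends on diagnosis, which is an interaction question. A covariate added on its own describes how subjects with PHN and DPN differ in NPRS change averaged over both treatments. Where the SAP wants an interaction it names one (week by treatment); none is named for diagnosis. The SAP text also specifies no treatment effect within PHN or within DPN.

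If the drug worked mainly in one condition, the planned output would give one pooled effect and a diagnosis coefficient that cannot be read as effect modification. Any estimate by diagnosis would come from the post-hoc clause, after database lock. Protocol 7.13.2 releases the randomisation schedule at that point, so the contrast could be chosen with allocations known. This sits poorly with promoting the analysis because the subgroups matter clinically.

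**Working it through.** **Inputs.** Protocol 13.2 and the synopsis give an SD of change of 2, a correlation between active and placebo response of 0.5, a difference of 1 unit, a two-sided 5% test, 90% power, 44 evaluable subjects and 20% dropout. The PHN/DPN split is not given, and the documents shown describe no stratification by diagnosis. The splits below are assumptions.

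**The plan's own figure.**
- SD of the within-subject difference = sqrt(2 × 2² × (1 - 0.5)) = 2.0.
- Normal approximation: n = (2 × (1.9600 + 1.2816) / 1)² = 42.03, so 43.
- Noncentral t at n = 44 gives power of 90.0%, and 44 / 0.8 = 55. The stated figures reproduce.

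**What the diagnosis term estimates.** Let g = 1 for PHN and 0 for DPN. Let d be the PHN-DPN difference in change on placebo (prognosis), t the drug effect in DPN, and h the extra drug effect in PHN. Leaving out period and baseline, the expected changes are:
- placebo: m + d·g
- LAT8881: m + d·g + t + h·g

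The within-subject difference is t + h·g, so d cancels. Only a treatment-by-diagnosis term recovers h. A main effect estimates the average over the two treatments, d + h/2:
- Effects of -2 in PHN and 0 in DPN, equal placebo response (d = 0, h = -2): coefficient -1.
- Same drug effect in both, prognostic difference of -1 (d = -1, h = 0): coefficient -1.
- Effects of -2 and 0, with placebo response offsetting (d = 1, h = -2): coefficient 0.

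**Precision of that coefficient at 22/22.** The variance of a subject's mean over the two treatments is 2² × (1 + 0.5) / 2 = 3. SE = sqrt(3/22 + 3/22) = 0.52, and power for a true value of -1 is about 46%.

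**Illustrative simulation** (40 runs per scenario, 44 subjects, 22/22, one change per treatment period):
- Effects -2 and 0 with offsetting placebo response: treatment effect -1.06 with or without the diagnosis term; diagnosis coefficient -0.08, significant in 7.5% of runs; interaction estimate 1.91 in absolute size, significant in 92.5%.
- Effect -1 in both diagnoses with a prognostic shift of 1.5 points: diagnosis term significant in 95% of runs, interaction in 7.5%.

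**What the interaction can deliver with 44 evaluable subjects.** SE = 2 × sqrt(1/n1 + 1/n2); power from the noncentral t with 42 df.

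| Assumed split | SE | 95% CI half-width | Power, 2 points | Power, 1 point |
|---|---|---|---|---|
| 22/22 | 0.60 | 1.22 | 90% | 37% |
| 35/9 | 0.75 | 1.51 | 74% | 26% |
| 40/4 | 1.05 | 2.12 | 46% | 15% |

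Within one diagnosis, the 95% CI half-width is t(0.975, n - 1) × 2 / sqrt(n):
- n = 22: 2.080 × 0.426 = 0.89
- n = 9: 2.306 × 0.667 = 1.54
- n = 4: 3.182 × 1.000 = 3.18

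**The case against.** The endpoint wording in Protocol 9.5 and SAP 7.5 asks only for an association between NPRS change and diagnosis, and a main effect answers that. The objective remains exploratory in a Phase IIa trial sized for the overall effect. The output goes to Table 14.2.10.1 of a Data Display Plan that is not among the documents, so a layout by diagnosis cannot be excluded. An interaction could also be run under the post-hoc clause. All of this stands. It limits the weight of the point, but it does not put a suitable term into the SAP text or answer the objective as worded.

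Two stronger readings are tempting and not supported:

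- A reader might infer that a drug working in one diagnosis only would leave no trace in the planned output. With equal placebo response the diagnosis coefficient would be about -1, with roughly 46% power at 22/22. There is a sign, but a non-specific one. It vanishes only if placebo responses happen to offset the drug effect.
- A reader might infer that adding diagnosis leaves the treatment estimate and its SE exactly unchanged. That holds only with complete data and no period-specific baseline. This model carries such a baseline, 20% dropout is expected, and SAP 9.2 defines the per-protocol set separately for each period. A further simulation (120 runs) with 20% of second periods missing gave a mean absolute shift in the treatment estimate of 0.021 (maximum 0.067). That is too small to rescue the analysis, but it is not zero.

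**Conclusion.** The point holds in this form: the analysis in SAP 11.6.2.5 cannot estimate whether the LAT8881 effect differs between PHN and DPN, and its diagnosis coefficient mixes prognosis with effect modification. It meets the endpoint's wording but not the placebo-comparative objective, nor the reason in SAP section 12 for its secondary status. This conclusion follows from the model's structure and does not depend on the simulations.

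The power and interval figures rest on the protocol's SD and correlation, on a simple analysis of within-subject differences, and on assumed splits; 22/22 is the most favourable of them. It would be wrong to infer that the primary result is compromised, because the primary model and its treatment contrast are untouched. The change is one the plan should make, not one the trial's main conclusion depends on.

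**What to change.** Before database lock, pre-specify a treatment-by-diagnosis term, with the contrast taken at week 4. Report the week 4 LAT8881-placebo difference with 95% CI within PHN and within DPN, and the interaction estimate with its CI. Label these as low-powered and exploratory in interpretation, and state the number of subjects in each diagnosis beside them. In the weekly model the week 4 contrast requires diagnosis to interact with treatment and week; if that is too thin for about 44 subjects, a model of week 4 alone is enough.

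Align the endpoint wording with the objective, so that both say whether the comparison with placebo is intended. State that the diagnosis main effect is not evidence of a difference in drug effect.

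The cost is a model term and a few output rows. The downside is wide intervals that need a caution, especially if one diagnosis is scarce.

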11.6.3 Exploratory Analyses

11.6.3.1

Descriptive summaries of average [REDACTED] will be presented by study period at Baseline and week 4 visits for test and control areas. This summary will be based [REDACTED]

[REDACTED] will be listed by subject.

In DDP: Table 14.2.11.1, Listing 16.2.6.7

11.6.3.1.1 *Mixed Effects Regression Model*

Mixed effects regression models will be used to compare the absolute change from baseline to week

The models will have fixed effects for period and treatment. Baseline score within each period by treatment combination will be included as a covariate. A random effect for subject will be included to capture the repeated measures nature of the design. Least squares mean changes from baseline and corresponding 95% CI will be presented for LAT8881, Placebo and the difference between LAT8881 vs. placebo overall. The null hypothesis that the difference in least square mean changes from baseline between LAT8881 and placebo across study periods is 0 will be tested. Statistical significance will be declared if the p-value for the difference between treatments < 0.05 . See Section 11.6.2.4.2 for SAS program.

In DDP: Table 14.2.11.2

11.6.3.2 NPRS and baseline variability

The model fitted to the change from baseline mean NPRS scores will be repeated by excluding subjects with highly variable baseline NPRS mean scores in first study period for Per-Protocol and FAS populations.

In DDP: Table 14.2.12.1 to 14.2.12.2

11.7 Safety Analyses

All safety summaries will be based on the Safety population. Screening visits will not be included in summaries, and will only be listed. Baseline measurements will be summarized under 'PreTreatment' for all safety summaries. EOS / Early Termination visits will be summarized in 'Total' within last treatment taken.

11.7.1 Adverse Events

All adverse events will be coded using the Medical Dictionary for Regulatory Activities (MedDRA) version 20.0 or later.

11.7.1.1 Overall Adverse Events

The number and percentage of subjects and number of events will be summarized by treatment overall and within each study period for the following categories:

1. All adverse events reported
2. Treatment emergent adverse events (TEAEs)
3. Serious adverse events
4. Serious treatment-emergent adverse events
5. Related treatment-emergent adverse events
6. Related treatment-emergent serious adverse events
7. Suspected unexpected serious adverse events (SUSARs)

8. Treatment-emergent adverse events led to death
9. Treatment-emergent adverse events led to study discontinuation

In DDP: Table 14.3.1.1.1, Table 14.3.1.1.2

The summary by treatment overall will only include 'New' events within each treatment. All adverse events will be listed by subject, system organ class and preferred term sorted by event start dates.

In DDP: Listing 16.2.7.1 to 16.2.7.5

11.7.1.2 Summary of Adverse Events by SOC and PT

The number and percentage of subjects and number of events will be summarized by treatment overall and within each study period, system organ class and preferred terms. The summary by treatment overall will only include both 'Ongoing' and 'New' AEs within each treatment and counted once in 'Total' column. Percentages will be based on the safety population. System organ class and preferred term will be displayed in the descending order of frequency of total number of events in LAT8881 group (both study periods).

The same will be for treatment-emergent AEs, treatment-emergent related AEs, treatment-emergent serious AEs and treatment-emergent related serious AEs. In DDP: Table 14.3.1.2.1 to Table 14.3.1.5.2

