10.9 Adverse Event Flags

Treatment emergent adverse event (TEAE) flags will be marked for adverse events if they occurred or worsened on or after the first administration of IMP in the first study period. Adverse events occurring during screening and first baseline period will not be considered as TEAEs.

If the events cannot be determined as TEAE due to partial dates, then the worst case will be considered and they will be flagged as TEAE in the respective study period based on AE start date.

Related Adverse Events will be flagged for Possibly, Probably and Definitely Related adverse events. Adverse events that started on or after first dose of IMP in treatment period 1 or during wash-out will be counted in the first treatment period and allocated to the treatment received in treatment period 1. AEs that commenced on or after first dose of IMP in treatment period 2 will be counted in the second treatment period and assigned to the treatment received in treatment period 2. If an adverse event occurred in first period and continued to second period, it will be counted in both study periods (as 'New' in period 1 and 'Ongoing' in period 2). If AEs have same month/year as IMP date, then the

decision regarding whether to consider them as 'Ongoing' or 'New' within the period will be decided in the blinded review meeting.

Suspected unexpected serious adverse events (SUSARs) will be flagged by the Sponsor and included in analyses datasets.

Programming note for adverse events:

- Period 1, Ongoing - if AE start date is prior to first dose of IMP in period 1 and end date is on or after first dose of IMP in period 1.
- Period 1, New - if AE start date is on or after first dose of IMP and before first IMP date in period 2.
- Period 2, Ongoing - AEs that were new or ongoing in period 1, with end date on or after first IMP date in period 2.
- Period 2, New - if AE start date is on or after first dose of IMP in period 2.

Adverse events will either be flagged in "Ongoing" or "New" within a study period, but not in both.

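### The SOC/PT adverse event tables count an event carried into Period 2 under both treatments, while the overall AE table counts it only under the treatment at onset

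*SAP*

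**What the plan says.** SAP 10.9 defines the flags. Events starting after the first Period 1 dose or "during wash-out will be counted in the first treatment period and allocated to the treatment received in treatment period 1". The same paragraph adds: "If an adverse event occurred in first period and continued to second period, it will be counted in both study periods", as 'New' in the first and 'Ongoing' in the second. The programming note defines Period 2 'Ongoing' as "AEs that were new or ongoing in period 1, with end date on or after first IMP date in period 2". The treatment-emergent flag is set for events "if they occurred or worsened on or after the first administration of IMP in the first study period", so it is anchored once, to Period 1.

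SAP 11.7.1.1 (overall AE table): "The summary by treatment overall will only include 'New' events within each treatment".

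SAP 11.7.1.2 (SOC/PT tables): "The summary by treatment overall will only include both 'Ongoing' and 'New' AEs within each treatment and counted once in 'Total' column". It then widens the scope: "The same will be for treatment-emergent AEs, treatment-emergent related AEs, treatment-emergent serious AEs and treatment-emergent related serious AEs".

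SAP 11.7.1.3 (SOC, PT and severity) also summarises by treatment overall but does not say whether 'Ongoing' events are included.

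**The concern.** There are two sequences and two treatments. A Period 2 'Ongoing' event that began after first dosing therefore began on the other treatment or in the off-drug interval that followed it. Including it in the Period 2 treatment's column credits that treatment with an event that was already present before it was given. The treatment-emergent flag does not screen it out, because that flag looks only at the first Period 1 dose. A causality flag of 'related' stays with the event too.

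Safety and tolerability is a stated objective, and SAP section 8 makes the safety analysis descriptive. The by-treatment columns of the SOC/PT tables are where a reader will compare LAT8881 with placebo for particular kinds of event. With few events expected per preferred term, one carried-over event can change a row.

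**Working it through.** The plan states no figure on this point, so there is nothing to reproduce. The check traces the flags and then illustrates the size.

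**Trace.** Take one event that starts after the first Period 1 dose and before the first Period 2 dose. Apply the 10.9 flags, then each table's rule.

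| Sequence | Present at first Period 2 dose? | 11.7.1.1: LAT8881 / placebo | 11.7.1.2: LAT8881 / placebo / Total |
|---|---|---|---|
| LAT8881 then placebo | yes | 1 / 0 | 1 / 1 / 1 |
| Placebo then LAT8881 | yes | 0 / 1 | 1 / 1 / 1 |
| LAT8881 then placebo | no | 1 / 0 | 1 / 0 / 1 |
| Placebo then LAT8881 | no | 0 / 1 | 0 / 1 / 1 |

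The tables differ only for events that span the first Period 2 dose, and then in both directions. Five categories appear under both rules: all AEs, TEAEs, related TEAEs, serious TEAEs and related serious TEAEs.

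**Size.** All rates here are assumptions.
- pL and pP are the proportions of subjects with a new event on LAT8881 and on placebo.
- c is the share of Period 1 onset events still present at the first Period 2 dose.
- The sequences are equal in size, everyone reaches Period 2, and onsets in the two periods are independent.

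Half the subjects take placebo second, and a share pL × c of them bring an event with them. The tabulated rates become:
- placebo: pP + 0.5 × c × pL × (1 − pP)
- LAT8881: pL + 0.5 × c × pP × (1 − pL)

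Subtracting, the products pL × pP cancel, which leaves (pL − pP) × (1 − c/2).

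With pL = 0.30 and pP = 0.20:

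| c | LAT8881 | Placebo | Difference |
|---|---|---|---|
| 0 | 30.0% | 20.0% | 10.0 points |
| 0.10 | 30.7% | 21.2% | 9.5 points |
| 0.25 | 31.8% | 23.0% | 8.75 points |
| 0.50 | 33.5% | 26.0% | 7.5 points |
| 1 | 37.0% | 32.0% | 5.0 points |

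For c = 0.25: placebo is 0.20 + 0.5 × 0.25 × 0.30 × 0.80 = 0.230, and LAT8881 is 0.30 + 0.5 × 0.25 × 0.20 × 0.70 = 0.3175. On the 44 planned completers, the placebo column gains 0.030 × 44 = 1.3 subjects and the LAT8881 column gains 0.0175 × 44 = 0.8. With equal true rates of 20% and c = 0.25, both columns rise to 0.20 + 0.5 × 0.25 × 0.20 × 0.80 = 22.0%, and the difference stays at zero.

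**The case against.** The strongest reply is that SAP 10.9 itself provides for counting a continuing event in both periods, so 11.7.1.2 applies a prespecified rule. That is fair as far as it goes. But the same paragraph allocates the event to the Period 1 treatment, and counting by period need not mean counting by treatment. Nor does it explain why 11.7.1.1 uses a different rule under the same column heading.

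A reader might infer that the plan hides a drug-related excess. The documents do not support that. Section 11.7.1.1 already reports onset-based counts of TEAEs, related TEAEs and serious TEAEs by treatment, all events are listed with start dates, and no safety test is biased. What is affected is attribution at SOC and PT level. A reader might also infer that the tables can never agree, but they do agree if no event spans the first Period 2 dose. Nor is the error aimed at placebo, since placebo-onset events enter the LAT8881 column in the same way.

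The size may well be small. An event that starts during dosing must outlast 21 days off drug (Days 29 to 49), although one that starts in the wash-out need not last so long. Protocol 7.11 and 11.1 provide for withdrawal after certain adverse events, and a 20% dropout is planned. Serious or treatment-limiting events are therefore the least likely to carry over.

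Finally, the sentence in 11.7.1.2 is garbled and closely resembles the concomitant-medication sentence in SAP 11.5, where counting ongoing use makes sense. It may be a drafting carry-over. It is still the current instruction, and section 12 of the SAP gives no reason for two rules.

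**Conclusion.** The point holds as a misattribution in the SOC/PT treatment columns and a conflict between two counting rules. Both follow from the SAP text without any assumption. The size does rest on assumptions. A true difference is attenuated by about 1 − c/2, which takes 10 points to between 9.5 and 7.5 for c from 0.10 to 0.50 at the assumed 30% and 20%. The documents supply neither the event rates nor c. Where the true rates are equal, both columns are inflated but the comparison is not distorted. The issue is worth correcting because these tables carry the event-level safety comparison and the correction is cheap. It does not undermine the trial's safety assessment as a whole.

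**What to change.** In SAP 11.7.1.2, assign each event in the by-treatment-overall tables once, to the treatment at onset, as 11.7.1.1 does. State that the same rule applies in 11.7.1.3.

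A bare 'New'-only filter is not enough, so add two exceptions and apply them in 11.7.1.1 as well so that the tables reconcile:
- Keep as a TEAE any pre-dose event that worsened after the first Period 1 dose. At UK sites, SAEs are recorded from consent (protocol 12.2), so such an event would be flagged 'Ongoing' in Period 1 and the filter would drop it.
- Count a carried-over event under the Period 2 treatment only if it worsened after the first Period 2 dose.

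Show the remaining carried-over 'Ongoing' events in a separate row or a listing, so that nothing is lost.

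The cost is a short SAP edit, a filter on flags that already exist, and a worsening rule added to the 10.9 programming notes, which now use start and end dates only. The rule must say how worsening is identified, because the AE data items listed in protocol 12.2 include intensity but no date on which it changed.
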